### 7.1.2 mITT (modified Intention to Treat) Analysis Set

The mITT analysis set is a subset of the ITT analysis set. The mITT analysis set will consist of subjects who have entered the hybrid closed-loop phase of the study successfully. The mITT analysis set will be used as the primary analysis set for all primary and secondary endpoints (both safety and effectiveness), and other clinical outcome data.

### 7.1.3 Per Protocol

The Per-Protocol (PP) analysis set is a subset of the mITT analysis set. Subjects will be included in the PP analysis set if they have a minimum of 80% system use during the hybrid closed-loop phase inclusive of manual and automated modes over a duration of 14 days and have completed the study without major protocol deviations. The PP analysis set will be used as supportive analysis for the effectiveness endpoints. The following will be considered major protocol deviations:

- Major inclusion/exclusion criterion deviation
- Significant protocol non-compliance that may confound the study objective data (e.g., use of prohibited medications)

The list of subjects excluded from the PP analysis set will be determined prior to analysis. If the PP analysis set does not differ from the mITT analysis set, separate analyses will not be presented.

## 7.2 CONTROL OF SYSTEMATIC BIAS

Several measures are incorporated into the study design to help minimize study bias as follows:

- 1) This is a multi-center trial to help ensure that investigator or site or subject enrollment bias is minimized. Selection of subjects will be made from the Investigator's usual subject load. Consecutively eligible subjects should be enrolled into the study.
- 2) This document specifies appropriate statistical methodology to ensure that bias is minimized.
- 3) The effectiveness measures will be based on the direct output from the device, ensuring objective reporting.
- 4) An independent Medical Monitor will adjudicate all SAEs and device related adverse events; the Medical Monitor's assessment of adverse events will be used for regulatory reports, product labeling, and publications or presentation.

## Statistical Analysis Plan

### 7.3 POOLING DATA ACROSS CENTERS

Up to 8 clinical sites will enroll subjects into the study. The analyses will be presented using data pooled across study centers. A formal assessment of the poolability of subjects across sites will not be performed.

### 7.4 CALCULATION OF PERCENTAGE OF TIME IN RANGE

Several effectiveness endpoints involve calculation of percentage of time in a specific glycemic range. These endpoints will be based on the direct output from a device (either a CGM or The Omnipod Horizon™ Automated Glucose Control System). The percentage of time in range (TIR) will be calculated as:

$$100 \times \frac{\text{\# of CGM records in range}}{\text{\# of evaluable CGM records}} = \text{TIR\%}$$

The following CGM records will be excluded from analysis, and therefore, from calculation of TIR endpoints:

- No glucose value is provided in the device output, such as due to an error or device deficiency during which the device does not record glucose readings
- CGM records reported prior to start of standard therapy phase or after subject's discontinuation from HCL

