**Table 1: Cohorts**

Cohort	Age Range	N (minimum)
Adults	14-70 years	18
Children	6-13.9 years	18

Following subject screening, enrollment, and device training, subjects will commence the outpatient standard therapy phase of the study.

Current Dexcom G6 CGM users may provide data from a 14-day period within the last 30-days. The CGM data meeting the minimum criteria must be the most recent data from the last 30-days. For non-G6 users, subjects will wear a study CGM, in blinded mode, to record glucose measurements over 14-days while subjects manage their diabetes at home per their usual routine while wearing a study CGM while remaining on their current MDI or pump therapy, and sensor, if applicable, for 14-days.

After completion of the standard therapy phase, subjects will be trained on the system and transition to the hybrid closed-loop phase initiating treatment with the Omnipod Horizon™ System.

Clinical site staff will receive alerts through a remote monitoring system during the hybrid closed-loop phase.

For the hybrid closed-loop phase, subjects will be divided into two groups:

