Dispense/Return Horizon System				X						X d		X
Complaints/device deficiencies				X e	X e	X e	X e	X e	X e	X e	X e	X e
Device uploads/Data review				X	X	X	X	X	X	X	X	X

Abbreviations: S=Screening; ST1=Standard Therapy Day One; ST2=Standard Therapy Day Two; HCL=Hybrid Closed-loop; EW=Early Withdrawal; QC=Quality Control Testing; Hotel/Rental House=HRH; UV=Unscheduled Visit

aEarly withdrawal visit will only be conducted for any subjects that started but did not complete the full study to include standard therapy and the hybrid closed-loop phase.

bUnscheduled visits will serve as extra study visits, if needed

cElectrocardiogram required for subjects >50 years old or with diabetes duration >20 years

dCollect only if subject is not extending their participation into the pivotal study

eDocumentation only applicable if there are changes from previous assessment

fVisits identified as "T/O" can either be conducted in person at the clinical site or over the telephone. Visits identified as "O" can only be conducted in person at the clinical site

gStudy device training for the CGM, blood glucose and ketone meters

hStudy device training for the Omnipod Horizon™ System

iSubjects deemed exempt from wearing the study CGM for 14-days will be eligible to immediately commence the hybrid closed-loop phase and may skip visit ST2

jAssessment of CGM criteria during screening applies to current Dexcom G6 users only

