### **Screening Assessments**

Subjects who have signed the informed consent and appear to meet the eligibility criteria will continue to the screening assessments which will be performed at the clinical study site.

Screening assessments must be completed within 30-days prior to the start date of the hybrid closed-loop phase (assessments do not need to be completed on the same day) and include the following:

- Medical history (including prior and current medical conditions and surgical history)
- Demographics (age, gender, race)
- A1C\*
- Thyroid Stimulating Hormone (TSH) level (local laboratory)
- Creatinine level (local laboratory)
- Pregnancy test for women of childbearing potential
- Review of concomitant medications
- Height
- Weight
- Assessment of vital signs
- Electrocardiogram (if applicable, see exclusion criteria 15)
- Questionnaire (Table 3: Questionnaires):
  - Clarke
    - Used to assess impaired awareness of hypoglycemia
- For Dexcom G6 users, assessment of whether subjects have met the CGM usage and data criteria to participate in an abbreviated standard therapy phase (Visit 2 only) per Table 2: Schedule of Assessments
  - At least 80% CGM use (11.2-days) during any consecutive 14-days in the past 30-days and
  - $\geq 2,016$  CGM values during the 14-days

\*Clinical sites will send the blood specimens for A1C to a NGSP (National Glycohemoglobin Standardization Program) certified central laboratory. A point of care (POC) A1C may be used to determine eligibility.

The Clarke Questionnaire will be administered during the screening visit. Subjects scoring  $\geq 4$  on the Clarke Questionnaire will require an overnight companion during the hybrid closed-loop phase. A companion is defined as someone who resides in the same home or building as the study subject and who can be available overnight.

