## **Enrollment**

Subjects who meet all eligibility criteria and have completed all screening assessments will continue to enrollment. A subject is enrolled in the study upon placement of the first study CGM. Subjects that do not meet the eligibility criteria will not continue in the study and will be considered screen failures.

If for any reason a subject is no longer eligible for the study after the standard therapy phase has commenced but prior to the commencement of the hybrid closed-loop phase, the subject will not continue in the prepivot study. No additional study assessments will be required. The reason for study exit will be clearly documented.

## 8 STANDARD THERAPY - PHASE 1

The standard therapy phase will commence after all standard therapy assessments are completed per **Visit 2** – see Table 2: Schedule of Assessments.

During the standard therapy phase, subjects will be asked to perform the following:

- Manage their diabetes at home per their usual routine
- Administer meal boluses per their usual dosing routine
- Change their sensor if a sensor fails, or as needed
- Calibrate their CGM, if required, per the manufacturer's instructions
- Monitor their capillary blood glucose (BG) per usual routine
- Give meal boluses. The timing of the bolus delivery will be per each subject's typical dosing routine.

Extending standard therapy past 14-days will not constitute a protocol deviation unless standard therapy extends past 30-days. If subjects extend beyond the 14-days, the most recent 14-days of data will be used in the endpoint analysis if the data meets the criteria defined for CGM use and data availability. If a subject enrolls into the pivotal study, data collected in the standard therapy phase will be used in the endpoint analyses for the pivotal study as the subject will not be required to repeat the standard therapy phase as part of the pivotal study.

The standard therapy phase will be customized depending on the following subject profile:

- Current Dexcom G6 users
- Non-G6 users
- Pump Naïve users

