### Current Dexcom G6 Users

Current Dexcom G6 users will be required to participate in the assessments required as part of standard therapy but may be exempt from wearing the study CGM for 14-days if the following criteria are met:

- Willing to provide 14-days of CGM data from the past 30-days
- Meet the success criteria of 80% CGM use during any consecutive 14-days in the past 30-days
- Must have  $\geq 2,016$  CGM values during the 14-days

If exemption criteria are not met, subjects may choose to continue to collect data until they meet the criteria or will be required to participate in the entire 14-day standard therapy phase consistent with the requirements for non-G6 users.

Subjects deemed exempt from wearing the study CGM for 14-days will be eligible to immediately commence the hybrid closed-loop phase.

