#### **8.1 Visit 2**

**Visit 2** represents the commencement of the standard therapy phase. All scheduled assessments will be performed according to Table 2: Schedule of Assessments. This visit will include:

- Review of concomitant medications
- Average total daily insulin (approximately over the past 7 days)
- Average total daily basal insulin (approximately over the past 7 days)
- Average total daily bolus insulin (approximately over the past 7 days)
- Review pump settings/MDI dosing
- Completion of questionnaires (see Table 3: Questionnaires for specific requirements by age group):
  - WHO-5
    - Used to measure current mental well-being
  - EQ-5D
    - Used to measure quality of life
  - T1DDS
    - Used to measure four critical dimensions of distress
  - DTSQs
    - Used to measure satisfaction with diabetes treatment regimens
  - Hypoglycemia Confidence Scale
    - Used to measure hypoglycemia unawareness, hypoglycemia frequency, severity and impact
  - HABS
    - Used to measure critical dimensions of hypoglycemia related concerns and confidence
  - PSQI
    - Used to measure sleep disturbance and usual sleep habits
  - IDSS (T1)
    - Used to measure patient satisfaction with their devices and impact on quality of life
  - SUS

- Used to measure usability of a system
- PAID-(Teen, Child)
  - Measures diabetes-related burden
- Training on Glucagon administration and information on treatment of hypo/hyperglycemia
  - All subjects are required to have access to glucagon and receive training on how to deliver the medication
- Study device training per manufacturer's instructions (CGM - blinded, BG, and ketone meters)
- Dispensing of CGM (blinded for non-G6 users), BG, and ketone meter
- QC testing of BG and ketone meter
  - Must pass at least one level of quality control testing prior to dispensing
- CGM sensor placement (if applicable)
  - Approved anatomical locations for CGM sensor placement will be reinforced as well as the importance of using approved locations

During this visit, subjects will be dispensed the following supplies:

- Dexcom transmitter
- Dexcom receiver
- Dexcom sensors
- Contour® Next One blood glucose meter
- Contour® Next One blood glucose meter test strips
- Contour® Next One blood glucose meter control solution
- Lancets
- Precision Xtra blood ketone meter
- Precision Xtra blood ketone meter test strips
- Precision Xtra blood ketone meter control solution

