### **11.3.2 Reportable Adverse Events**

Adverse events will be assessed on an ongoing basis throughout the study. Adverse event reporting will begin at the start time of the standard therapy phase (i.e., insertion of the CGM sensor) and continue through the hybrid closed-loop phase until the subject's participation has ended. All adverse events must be followed until resolution, or until the AE has stabilized, or until the study has been completed.

Pre-existing medical conditions or symptoms observed prior to the start time of the standard therapy phase will not be recorded as an AE and should be collected in the subject's medical history. In the event there is a change (i.e., worsening) in the pre-existing medical condition or symptoms after enrollment meeting the criteria of a reportable adverse event, then an AE must be reported.

For this protocol, a reportable adverse event includes any untoward medical occurrence that meets one of the following criteria:

1. An SAE
2. An ADE unless excluded from reporting in Hypoglycemic Events and Hyperglycemic/Ketotic Events sections below
3. An AE occurring in association with a study procedure
4. An AE not related to a study device issue which leads to temporary or permanent discontinuation of the study device
5. An AE that affects the participant's ability to complete any study procedures
6. An AE for which a visit is made to a hospital emergency department
7. Hypoglycemic Events as defined below
8. Hyperglycemic/Ketotic Events as defined below.

Skin reactions from sensor or pod placement are only reportable if severe and/or required treatment.

For the purpose of this protocol, mild symptoms of hypoglycemia and hyperglycemia (i.e., clinically non-significant) or blood glucose values out of the normal range (whether or not they resulted in delayed meals or correction boluses) will not be reported as AEs unless determined to meet the reportable criteria in the Hypoglycemic Events and Hyperglycemic/Ketotic Events sections below.

All reportable AEs—whether volunteered by the participant, discovered by study personnel during questioning, or detected through physical examination, laboratory test, or other means—will be reported on an AE eCRF.

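### Read literally, the SAP's TIR exclusion rule drops the retrospective 14-day baseline of exempt Dexcom G6 users from the primary paired comparison

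*SAP*

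**What the plan says.** SAP Section 7.4 lists the CGM records left out of every TIR calculation. One item is "CGM records reported prior to start of standard therapy phase or after subject's discontinuation from HCL". It has no exception. The SAP does not say when standard therapy starts and does not mention retrospective CGM data. SAP Section 1 states that the SAP prevails where it differs from the protocol.

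The protocol dates the start of the phase in these places:

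- Section 8: "The standard therapy phase will commence after all standard therapy assessments are completed per" Visit 2.
- Section 8.1: Visit 2 "represents the commencement of the standard therapy phase".
- Section 11.3.2, for adverse event reporting: "start time of the standard therapy phase (i.e., insertion of the CGM sensor").

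For current G6 users it provides a shorter route:

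- Section 7.1, Screening Assessments: those who meet the CGM criteria "participate in an abbreviated standard therapy phase (Visit 2 only").
- Table 2, footnote: exempt subjects "will be eligible to immediately commence the hybrid closed-loop phase and may skip visit ST2".
- Section 8, Current Dexcom G6 Users, exemption criterion: "Willing to provide 14-days of CGM data from the past 30-days".
- Section 5.2: "The CGM data meeting the minimum criteria must be the most recent data from the last 30-days".

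The primary comparison is a paired t-test of standard-therapy TIR against HCL TIR (SAP 4.2). Analyses use available data only, without imputation (SAP 7.5). Protocol Section 12.4 also asks for the primary effectiveness endpoint by G6 use at screening.

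**The concern.** The protocol intends the supplied 14 days to be the baseline of an exempt G6 user. The SAP's exclusion depends on a start date that falls after those days, so it removes the records the comparison needs.

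An exempt user then has no standard-therapy TIR and cannot form a pair. If Visit 2 falls some days before HCL start and records from the subject's own device continue and are collected, the subject has only a stub as baseline. SAP 7.4 sets no minimum record count that would catch this.

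The loss is also selective. It removes experienced G6 users, so it changes who is in the primary comparison as well as its precision, and it could largely empty the paired results for G6 users. The secondary time-in-range endpoints use the same method (SAP 6.1) and are affected in the same way. HCL-only summaries and safety are not.

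**Working it through.** **Step 1: do the retrospective records predate the phase?**

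| Possible start of standard therapy | Source | Are the supplied 14 days inside the phase? |
|---|---|---|
| Visit 2 | Protocol 8 and 8.1 | No. They are assessed at screening (Visit 1), ordinarily before Visit 2 |
| CGM sensor insertion | Protocol 11.3.2 (adverse events) | No. Table 2 lists sensor placement at Visit 2, and exempt users need not wear the study CGM |

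Applying the second definition to a personal sensor worn before screening would start adverse event reporting before consent, so it cannot be meant that way. Neither definition keeps the data.

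**Step 2: how many pairs are at risk?** The plan gives no power, effect size or SD to reproduce; its sample size is not hypothesis-driven. The inputs are 36 planned evaluable subjects, 18 per age cohort (SAP 4.1), and 16 in Group 1, 8 per cohort (SAP 2.3). Protocol 5.2 anticipates that Group 1 will consist only of G6 users. Not every G6 user need be exempt, so 16 is an upper bound for Group 1. The middle row below (4 exempt per cohort) is an assumption, and all three rows assume nobody in Group 2 is exempt.

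The 95% half-width for a mean paired change, in units of its SD, is t(0.975, n−1)/√n.

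| Exempt | Pairs, pooled | Half-width, pooled | Pairs per cohort | Half-width per cohort |
|---|---|---|---|---|
| 0 | 36 | 0.338 | 18 | 0.497 |
| 8 | 28 | 0.388 | 14 | 0.577 |
| 16 | 20 | 0.468 | 10 | 0.715 |

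From the first row to the last, the interval widens by 0.468/0.338 = 1.38 times pooled and 0.715/0.497 = 1.44 times per cohort. Exempt Group 2 subjects would add to this: with 24 exempt in all (assumed), 12 pairs remain and the pooled half-width is 0.635, or 1.88 times the full-data value.

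**Step 3: on the TIR scale.** The documents give no SD of the paired change. Assuming 10 percentage points (range 8 to 12), the per-cohort half-widths are:

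- 18 pairs: 0.497 × 10 = 5.0 points (4.0 to 6.0)
- 14 pairs: 0.577 × 10 = 5.8 points (4.6 to 6.9)
- 10 pairs: 0.715 × 10 = 7.2 points (5.7 to 8.6)

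**Step 4: the stub.** SAP 6.2 gives about one record every 5 minutes, so 1,440/5 = 288 records a day. The protocol's baseline criterion is at least 2,016 values, and 2,016/288 = 7.0 days. Any stub shorter than 7 days therefore fails the protocol's own criterion, yet would enter the SAP's TIR calculation unchecked.

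**The case against.** The strongest reply is that this reading is not forced. The SAP is silent on when standard therapy starts. If the protocol fills that gap, it should also supply the data source, and Protocol 5.2 describes the supplied window in its account of standard therapy. SAP 2.3 speaks of a 14-day phase with no abbreviated form, and for an exempt user the only such 14 days are the supplied ones. An analyst would see the missing pairs and correct the programming. The size rests on an unknown number of exempt subjects and an assumed SD, and 36 is a minimum, with up to 48 enrolled. The study has no hypothesis or success criterion, and the decision to open the pivotal study to further subjects rests on a safety review.

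Much of this stands. The protocol's intent is clear and the exclusion is probably unintended. The size is conditional, and with no exempt subjects there is no loss. No pass/fail decision is affected.

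It does not remove the point. No sentence in either document places the supplied window inside the phase. Limiting the phase to Visit 2 for exempt users points the other way, and the precedence clause favours the SAP's text. Relying on an analyst to notice leaves the choice of baseline records to be made after the data are in hand, in an unblinded single-arm study.

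**Conclusion.** The concern holds. SAP 7.4 states a rule that, applied as written, removes the intended baseline of every exempt G6 user whose supplied data predate Visit 2. Up to 16 of 36 planned pairs (16/36 = 44.4%) could be lost from Group 1, and more if Group 2 includes exempt users. The half-widths depend on the assumed number exempt, and those in TIR points also on the assumed SD. Because 36 is a minimum and the mITT set takes everyone who enters HCL, the pair counts are illustrative. What is affected is the population and precision of the primary effectiveness comparison, the secondary time-in-range comparisons and the presentation by G6 use. This should be fixed before analysis.

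**What to change.** Replace the exclusion in SAP 7.4 with a standard-therapy window defined for each subject: the most recent consecutive 14 days before HCL start that meet the protocol's CGM criteria (at least 80% use and at least 2,016 values, with the 30-day limit stated), whether collected prospectively or supplied by an exempt G6 user. Then exclude standard-therapy records outside that window and records after discontinuation from HCL.

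This also settles how two protocol phrases fit together. The reference to any consecutive 14 days (Sections 7.1, 8 and 8.2) determines which periods qualify; the reference to the most recent data (Sections 5.2 and 8) determines which qualifying period is used. A stub shorter than 7 days could no longer serve as baseline.

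The cost is SAP wording and programming. The protocol already requires exempt users to supply the data, so no new data, visits or subjects are needed.

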### 7.5 HANDLING OF MISSING DATA

All practical monitoring and follow-up steps will be taken to ensure complete and accurate data collection. It is anticipated that the rate of missing data would be very low due to the limited duration of the study. All analyses will be based on available data only; no imputation for missing data is planned.

### 7.6 OTHER DATA SUMMARIES

The distribution of each baseline characteristic or demographic parameter of interest (such as age, gender, medical history, etc.) will be presented. Data on all enrolled subjects will be presented. If a considerable number of subjects do not enter the HCL phase of the study, these results may also be presented for the mITT and/or PP analysis sets. Continuous variables will be summarized using count, mean, median, standard deviation, and range. Categorical variables will be summarized using counts and percentages.

Statistical testing will be performed to assess significant change from Baseline in various measures. Any testing performed will be based on one-sample t-test for continuous variables, or chi-square test or Fisher's exact test for categorical variables, using a two-sided significance level of 5%. If the

